6.3 Safety Measures

6.3.1 C-SSRS (Columbia Suicide Severity Rating Scale)

The C-SSRS is a clinician-administered measure of suicidal behavior devised to detect potential suicidal thoughts or behaviors during a clinical trial [74]. In this study, the Since Last Visit version will be used. The first assessment will measure suicidality since the last administration in the parent study and for the previous two weeks. All subsequent administrations will assess suicidality since the last administration in this protocol. The C-SSRS assesses suicidal ideation, ideation intensity, and behavior and consists of a series of questions and can be administered during a face-to-face interview or over the telephone. Participants who are discontinuing medications to participate in the study will complete the C-SSRS before and after medication washout. The C-SSRS Intensity scale for Lifetime obtained a Cronbach's alpha of 0.93 and 0.94 for the Since Last Visit form, and Last Visit C-SSRS severity scores were positively correlated with the BDI "suicide thoughts" item [75]. The MAPS Adapted C-SSRS was developed utilizing [name] Columbia Suicide Severity Scale. The MAPS Adapted C-SSRS maintains the content and flow of the standard C-SSRS. The scale was adapted to modify formatting and add additional administrative guidance to reduce rater and data entry errors. The MAPS Adapted C-SSRS has been approved by [name] for use in MAPS Research and is referred to throughout the protocol as C-SSRS. The MAPS Adapted C-SSRS takes approximately 10 minutes to complete.

6.4 Screening Measures

6.4.1 MINI (Mini-International Neuropsychiatric Interview)

This version of the MINI (7.0.2), a structured interview that was first developed in 1998 to be compatible with DSM and International Classification of Disease (ICD) criteria for psychiatric illnesses [76], is now compatible with DSM-5 and will be administered by a member of the Independent Rater (IR) Pool to screen for psychiatric conditions per DSM-5. Each module of the MINI consists of two or three questions

where the answer is either "Yes" or "No," and decision-tree logic is used to determine whether to ask additional questions [77]. The MINI takes around 75 minutes to perform and addresses major psychiatric disorders. MINI items were highly reliable (interrater reliability between kappa of 0.8 and 0.99; test-retest reliability between 0.6 and 0.9 for all scales save "current mania), and diagnosis via MINI was comparable to that made with the Composite Diagnostic Interview and the SCID [77, 78] Testing on nonpsychiatric samples did not create false positives [76]. The IR pool will not assess the PTSD or Antisocial Personality Disorder modules.

6.5 Exploratory Measures

6.5.1 LEC-5 (Life Events Checklist for DSM-5)

The LEC-5 is a 17-item self-report instrument designed to determine the presence of traumatic life events in the assessment and diagnosis of PTSD. It is a companion measure to the PCL-5 and will be used to assess PTSD as well as presence of other life stressors. The participant indicates whether each event listed has occurred since the last administration of the measure (in parent study), permitting the possibility of marking multiple events [79].

6.5.2 BDI-II (Beck Depression Inventory II)

The BDI-II is a revision of the BDI, a 21-item self-report measure [80, 81] that will serve as a measure of depression symptom severity over the prior 2 weeks [82]. The BDI-II has been validated, has high internal consistency and good test/re-test reliability, and is not overly sensitive to daily variations in mood. It takes 5 to 10 minutes to complete [82]. Score cutoffs indicate: 0 to 13 minimal depression, 14 to 19 mild depression, 20 to 28 moderate depression, and 29 to 63 severe depression. Initial and subsequent studies report that the BDI-II total score has a reliability coefficient of 0.90 to 0.91 which is related to other measures of depression symptoms [82, 83]. Higher scores indicate more severe depressive symptoms.

6.5.3 CPGS (Chronic Pain Grade Scale)

The CPGS is a seven-item measure of pain. Responses to six of the seven items are made on a 10-point Likert scale regarding pain intensity in the past 6 months, and the response to the other item is made on a 10-point Likert scale regarding present-day pain [84]. Responses to questions are used to attain a rating (grade) for pain from 0 (no pain) to five (high disability, severely limiting). The instrument has three scale scores: pain severity, pain intensity, and pain-related disability. Estimated time to complete is 3 to 5 minutes. The CPGS is a validated scale with high internal consistency (Cronbach's alpha=0.90) and correlated with other instruments assessing pain [85].

6.5.4 EQ-5D-5L (EuroQol Five Dimensions-Five Levels Questionnaire)

The EQ-5D-5L is a two-part self-report questionnaire assessing health status. It consists of five dimensions; mobility, self-care, usual activities, pain-discomfort and anxiety-depression, and one visual analog scale (VAS). Responses are made on each dimension by checking one of five statement that best reflects their health on the day of measure completion, from the healthiest or fewest problems (e.g., "I have no trouble walking about") to the most trouble (e.g., "I am unable to walk about") [86, 87]. In the second part of the EQ-5D-5L, current degree of health ("your health today") is indicated by marking a 20 cm line marked form one to 100, with 100 considered "the best health you can imagine" and one "the worst health you can imagine." The EQ-5D-5L does not sum responses but treats each response on a dimension as a scale score, and the VAS is the location of the mark in centimeters. The scale can permit comparison across groups on health profiles, and an index can be derived from matching the five-dimension scores and the VAS response with nation-specific datasets and calculator software or statistical

software syntax designed for the measure. The EQ-5D-5L began as part of the EuroQoL measure, published in 1990 [88]. The instrument has been validated in populations from eight countries. EQ-5D-5L index scores and VAS scores assessed in people with stroke varied with degree of recovery assessed via long-term observation. EQ-5D-5L index scores and VAS scores assessed in people with stroke varied with degree of recovery assessed via long-term observation [89]. The EQ-5D-5L takes about 3 minutes to complete.

6.5.5 AUDIT (Alcohol Use Disorders Identification Test)

The AUDIT is a ten-item self-report test covering alcohol use habits over the past year. Respondents answer on a 5-point scale (0=Never or none, 4=Daily or greatest number) [90]. The ninth item addresses occurrence of injury of self or other as a result of drinking and the tenth addresses others' concerns about the respondent's drinking, with only three responses provided (0=No, 2=Yes, but not during the last year, 3=Yes, during the last year). The measure can readily detect alcohol abuse disorders in a wide array of individuals [91].

6.5.6 DUDIT (Drug Use Disorders Identification Test)

The DUDIT is an 11-item measure designed to assess presence of substance use disorders within the past year [92]. Responses to items are made on a 5-point scale with exact responses varying across questions. When present, use can be described in monthly or less than monthly versus four times a week or daily. A list of substances is provided at the end of the measure. The DUDIT is reliable, with a Cronbach's alpha of 0.80. When compared with an interview based on ICD 10, the DUDIT had a sensitivity to detecting substance use disorders of 90% and a specificity of 80% [92]. The English translation was developed from a Swedish-language original. Estimated time to complete is 2 to 4 minutes.

6.5.7 SRNU (Self-reported Nicotine Use)

The SRNU is a sponsor-developed measure that will assess participant's use of nicotine, including approximate frequency of use in the last month and attitudes towards quitting. The measure will take less than 3 minutes to complete.

6.5.8 EAT-26 (Eating Attitudes Test)

The EAT-26 is a 26-item self-report measure that assesses attitudes about eating and food currently and is used to assess presence of eating disorders [93]. Responses are made on a 6-point scale (1=Always to 6=Never), and gathers information on gender, age, height, and weight. The EAT-26 produces a total score and can be used to generate a "referral score." The 27th item addresses the occurrence and frequency of specific eating behaviors, such as binge eating. Estimated time to complete is 4 to 8 minutes. Items on the EAT-26 have high reliability coefficients (Cronbach alpha of 0.83 to 0.90) and has concurrent validity [94].

6.5.9 HPOSF (Health and Work Performance Absenteeism and Presenteeism Short Form)

The HPQSF is a short form of a larger measure of health and work performance that has selected items referring to absenteeism and work performance [95]. The larger measure was created by the WHO as part of the Global Burden of Disease initiative. It consists of eight questions selected from the larger Health and Work Performance Questionnaire, with one question containing five additional items. Items include questions concerning hours worked during an average week, number of whole and partial days missed during a 4-week period, and items that rate average coworker and self-work performance on a ten-point Likert scale (1=Worst performance to 10=Top performance). Hours spent in work over a 4-week period

and over the last 7 days can be used to estimate absenteeism, and the HPQSF can also score presenteeism, a measure of actual performance in relation to possible performance. Self-reports on measure appear to match employer records of presence or absence [96], and the HPQSF appears to be reliable between one time point and another (reliability of 0.52) and is sensitive to change [95].

6.5.10 UFEC (Utilization of Facility-based and Emergent Care)

The UFEC is a sponsor-developed measure assessing participant health events, including hospitalization and use of healthcare facilities, including in-patient hospitalization, rehabilitation facilities and other health care facilities since termination from the parent study.

7.0 Study Procedures

All assessments must be performed by qualified study staff delegated these duties on the Site Responsibilities Log. The Clinical Research Associate (CRA) should be notified of any delays or deviations to study procedures and Medical Monitor consulted if necessary. If there are delays of more than 7 days between visits or contact, the site should assess the need for additional telephone contact with the participant to ensure safety.

Table 5: Time and Events-Study Procedures

		Screening Period (1 to 6 weeks)		Preparatory Period (At least 5 days, depending on medication tapering)							
		Screening			Prepa	aratory					
Visit	Phone Screening	Screening	IR Screening	V0	V1	V2	V3				
Visit Description	Phone Calls	In-person/Remote Visits & Labs	Telemedicine	Enrollment	Prep. 1	Prep. 2	Prep. 3				
Visit Timing	Prior to Initial Screening	Over 7 to 70 days	After initial screening visit	2 to 14 days post IR Screening	0 to 14 days after V0	At least 2 days after V1 (depending on tapering)	Post V2 & Taper; 1 to 14 days before V4				
Initial Phone Screen	✓										
Informed Consent	Send Copy	✓									
Follow-up Phone Screen	✓										
Assess Eligibility	✓	√	✓	✓	√	✓	✓				
Medical/Psychiatric History	✓ A	✓			✓	✓	✓				
Past/Current Medication &	✓	✓		✓	✓	✓	√				
Adherence											
Weight		✓									
Resting Vitals		✓									
Physical Exam		✓									
ECG & Rhythm Strip		✓									
Clinical Lab Tests		✓									
Drug Screen		✓					✓				
Pregnancy Screen		✓					✓				
Enter Participant in eCRF		✓									
Independent Rater Assessment			✓								
Medication Taper				✓	√	√					
Study Enrollment				✓		_					
All AEs ^B				✓	√	✓	✓				
90-min Preparatory Session					✓	✓	✓				
Phone Call Follow-up ^C						✓					
Measures (ePRO or Clinician- Administered D		√	✓		√	√	√				

A At Screening, collect data on previous hospitalizations and healthcare utilization. Site physician may request participants to obtain medical/psychiatric records generated since the end of the parent study as required for eligibility assessment

B All Adverse Events (AEs) includes collecting Serious Adverse Events, AEs of Special Interest, AEs of Psychiatric Status, AEs requiring medical advice or attention, AEs that indicate withdrawal of a participant, and all other AEs

^C If needed, call participant to confirm medication tapering and stabilization is complete prior to Visit 3 ^D Refer to Table 6: Time and Events-Measures for details

	Treatment Period 8 to 20 weeks Treatment 1 Treatment 2 Treatment 3													
		Tres	atment 1			Trea	tment 2				Study Termi- nation			
Visit	V4	V5	V6	V7	V8	V9	V10	V11	V12	V13	V14	V15	V16	
Visit Description	Exp. 1	Int. 1.1	Int. 1.2 F	Int. 1.3 ^F	Exp. 2	Int. 2.1	Int. 2.2 F	Int. 2.3 ^F	Exp. 3	Int. 3.1	Int. 3.2 ^F	Int. 3.3 ^F	Study Termination	
Visit Timing	1 to 14 days after V3	Morning after V4	10 to 18 days after V4	At least 2 days after V6; 1 to 14 days before V8	21 to 56 days after V4	Morning after V8	10 to 18 days after V8	At least 2 days after V10; 1 to 14 days before V12	21 to 56 days after V8	Morning after V12	10 to 18 days after V12	At least two days after V14	24 to 32 days after V12	
Past/Current Medication & Adherence	√	√	√	√	√	√	~	√	√	✓	√	~	✓	
Drug Screen	✓				✓				✓					
Pregnancy Screen	✓				✓				✓				✓	
All AEs A	✓	✓	✓	✓	✓	✓	✓	√	✓	✓	√	✓	✓	
Container Assignment ^B	√				✓				√					
Administer IMP	✓				✓				✓					
At least 6-hour Exp. Session	√				√				√					
BP, Pulse, Temperature	√ c	✓ H			√c	✓ H			√c	✓ H			✓ D	
Potential Overnight Stay	√				√				√					
90-min Integrative Session		√	√	√		√	√	√		√	√	√		
Phone Call Follow-up ^E		√				√				√				
Weight			-										√	
Measures (ePRO or Clinician- Administered ^G	√	✓ E	√	√	√	✓ E	√	· C.D. · Listois	√	✓ E	√ 1:11.:.	√	√	

All Adverse Events (AEs) includes collecting Serious Adverse Events, AEs of Special Interest, AEs of Psychiatric Status, AEs requiring medical advice or attention, AEs that indicate withdrawal of a participant, and all other AEs

^B Obtain container assignment 24 to 48 hours prior to each Experimental Session

^C During Experimental Sessions, vitals are measured within 15 minutes before Investigational Product administration, immediately before the supplemental dose is administered (or would be, if supplemental dose not given), and approximately 6 hours after initial dose, and as needed. Additional measurements to be taken if clinically indicated (e.g., if blood pressure does not return to baseline).

^D At Study Termination, only blood pressure needs to be measured

^E 14 days of phone call follow-up: every other day after the Experimental Session; includes C-SSRS administration and AE collection

F All Integrative Sessions must be at least 2 days apart

^G Refer to Table 6: Time and Events-Measures for details

^H If clinically indicated.

MAPPUSX Protocol Amendment 3 Version 1: 15 March 2023

Table 6: Time and Events-Study Measures

	Screenin		Screening Preparatory Period			Treatment 1			Treatment 2			Treatment 3				Study Termi nation			
	Visit #	Screening	IR Screening	V1	V2	V3	V4	V5	V6	V7	V8	V9	V10	V11	V12	V13	V14	V15	V16
Visit Description	~Time to Complete Measure (minutes)	Site Visit	Tele- medicine	Prep. Session	Prep. Session 2	Prep. Session	Exp. Session 1	Int. Sessions 1.1	Int. Session 1.2	Int. Session 1.3	Exp. Session 2	Int. Sessions 2.1	Int. Session 2.2	Int. Session 2.3	Exp. Session 3	Int. Sessions 3.1	Int. Session 3.2	Int. Sessi on 3.3	Study Termi- nation
C-SSRS A	10	✓	✓			✓	✓ B	✓	√	✓	✓ B	✓	✓	✓	✓ B	✓	✓	✓	✓
MINI	75		✓																
LEC-5	5	✓				✓			✓				✓				✓		√
PCL-5	8	✓				✓			✓				✓				✓		√
SDS	5					✓													√
BDI-II	5					✓													✓
CPGS	5					✓													✓
EQ-5D-5L	3					✓													✓
AUDIT	3	✓																	✓
DUDIT	3	✓																	✓
SRNU	3					✓													✓
EAT-26	6					✓													√
HPQSF	5					✓													√
UFEC	3	✓																	
~Total Time of Completing Measures (minutes)	139	29	85	0°C	0°C	55	90 ^B	10	23	10	90 B	10	23	10	90 ^B	10	23	10	61

A All C-SSRS are Since Last Visit. The first assessment will measure suicidality since the last administration in the parent study and the last two weeks. All subsequent administrations will assess suicidality since the last administration in this protocol.

^B Conducted pre- and post-Investigational Product administration, and every other day for 14 days after Experimental Sessions.

^C No planned measures to be assessed at Visit 1 or Visit 2

Amendment 3 Version 1: 15 March 2023

MAPPUSX Protocol

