During one of the Preparatory Sessions, if possible, the therapy pair will introduce the participant to the attendant who will remain with the participant during each overnight stay after each MDMA-assisted therapy session. The attendant will be an individual with previous training in caregiving. The site will make all attempts to have the same attendant for each Experimental Session for a given participant, but it is not guaranteed.

7.2.1 Preparatory Sessions 1 and 2

Preparatory Session 1 (Visit 1) will occur 0 to 14 days after Visit 0. The visit timing should take in to account appropriate times for monitoring medication tapering.

Preparatory Session 2 (Visit 2) will occur 2 to 75 days after Visit 1. The visit timing should take into account appropriate times for monitoring medication tapering.

If tapering is ongoing at Preparatory Session 2 (Visit 2), the site team will schedule a telephone phone call within 7 days of completion of tapering and stabilization. If tapering is complete or not needed, the site team will confirm eligibility and schedule Preparatory Session 3 (Visit 3) as soon as possible.

7.2.2 Preparatory Session 3

Preparatory Session 3 (Visit 3) should take place as soon as possible after medication tapering and stabilization and 1 to 14 days prior to Experimental Session 1 (Visit 4).

The site team will confirm eligibility and ensure that the participant continues to agree to all lifestyle modifications. If any requirements are not met before or during Visit 3, the participant will be considered a Pre-Treatment Early Termination.

For eligible participants, qualified site staff will:

- Perform urine pregnancy test for participants who are able to become pregnant.
- Perform urine drug test.
- Administer Since Last Visit C-SSRS to determine suicidal risk.
- Actively support participant in the completion of Baseline self-reported measures. Completion of measures does not need to be recorded.
 - PCL-5, under the direction of the therapy pair, who will remind them of the index trauma identified in the parent study to which PTSD symptoms should be anchored

- o LEC-5
- o SDS
- o BDI-II
- CPGS
- o EO-5D-5L
- o SRNU
- o EAT-26
- o HPQSF
- Complete the third 90-minute Preparatory Session with the purpose of confirming all enrollment eligibility is met and completing final preparation for the first Experimental Session.
- Remind the participants of lifestyle modifications, including fasting and refraining from using

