medications may	blunt the effects of MDMA-assisted
result in increase	therapy. Therefore, ongoing
in severity of	psychiatric medications must be
underlying	tapered and stopped at least five half-
psychiatric	lives of parent drug or active
symptoms or	metabolite (whichever is longer)
other adverse	prior to Visit 3. For non-selective
events	irreversible MAOIs, a 2-week
	washout period following the taper is
	required (3 weeks in the case of
	imipramine and clomipramine,
	tricyclic antidepressants with MAOI
	activity) prior to the Visit 3. The
	tapering and withdrawal of such
	medications can lead to new or a
	return of symptoms these medications
	were initially prescribed to treat and

has been known to induce suicidal ideation or behavior in some people.

- Participants will be informed of the potential risks associated with medication taper and cessation, and will be encouraged to discuss this with the prescribing clinician.
- Study clinicians are encouraged to contact the prescribing clinician (with participant consent) and discuss the tapering plan.
- Participants will be closely monitored during the medication tapering and AEs will be recorded.
- Should a participant be unable to successfully taper off any prohibited medication, the participant will be withdrawn from the study and referred back to the prescribing clinician for evaluation and possible restart of psychiatric medication.
- Participants are informed at screening that they should not initiate tapering themselves or
 with their prescribing clinician for study participation to ensure that the tapering plan is
 monitored by the site clinician and Medical Monitor.

Other

Suicide and Risk of Self-Harm

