Suicidal ideation and behavior are disease related events with high incidence in populations of people with PTSD, especially those suffering from chronic PTSD. Due to the nature of the therapeutic method, wherein a person may re-experience emotions associated with the traumatic event in order to reprocess the memory in a new, therapeutic way, thoughts of ending one's life may surface during the process. In previous MAPSsponsored clinical trials C-SSRS scores have escalated during the Preparatory Sessions, which is thought to be a result of preparatory discussion of traumatic experiences, and/or participants concomitant tapering off long-prescribed medications, such as SSRIs and benzodiazepines. During both non-drug and MDMAassisted therapy sessions, participants are asked to think about and discuss their experiences, thoughts, and emotions related to their condition. Participants are also asked to report on their suicidality in these sessions and follow-up phone calls through C-SSRS administration. They may experience intense emotional responses to recalling and speaking about this material. As MDMA is only administered in combination with therapy, the distress associated with therapy is unavoidable and is considered a necessary part of the therapeutic process that requires proper facilitation and support from

therapists.

- Therapy teams minimize risks by carefully evaluating all participants to determine if there is a current risk of suicidal behavior. Participants with current, severe suicidal ideation or a suicide attempt within the past six months are excluded from the trial, see Section 3.2
 Exclusion Criteria. However, participants with a history of suicide attempts are not excluded unless significant risk of suicidal behavior is present at the time of Screening, as this would result in enrolling a non-representative sample of the population.
- If positive serious ideation or behavior occurred after study enrollment, the investigators are to make additional follow-up C-SSRS observations to ensure participant safety and to track scores until they returned to non-serious levels.
- Should a participant be at serious risk to themselves, then the therapy team and site staff will intervene appropriately, consistent with professional practice standards. In extreme circumstances, this may involve summoning external crisis management teams for further assessment which may lead to involuntary hospitalization.

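### No C-SSRS is scheduled between Independent Rater Screening and Visit 3, so the medication taper has no routine structured screen for suicidality

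*Protocol*

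**What the plan says.** Table 6 (Protocol 7.0) ticks the C-SSRS at Screening, IR Screening and Visit 3, then at every visit from Visit 4. Visits 1 and 2 carry zero minutes of measures, with the footnote "No planned measures to be assessed at Visit 1 or Visit 2". Visit 0 has no column. The SAP's measures table (SAP 5.0) has the same ticks and footnote. Protocol 7.2.1, on Preparatory Sessions 1 and 2, orders no form. At Visit 3, 7.2.2 tells staff: "Administer Since Last Visit C-SSRS to determine suicidal risk".

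Protocol 11.3 starts the taper at the enrollment visit, and 4.2 wants psychoactive tapers finished before Visit 3.

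Table 9 (Protocol 9.1) says of tapering and withdrawing psychiatric medication that it "has been known to induce suicidal ideation or behavior in some people". It also reports that in earlier sponsor trials "C-SSRS scores have escalated during the Preparatory Sessions", and attributes this to preparatory discussion of trauma, to taper, or to both.

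The stated protections include "Participants will be closely monitored during the medication tapering and AEs will be recorded" and, in 7.0, "If there are delays of more than 7 days between visits or contact, the site should assess the need for additional telephone contact". Table 9 adds: "If positive serious ideation or behavior occurred after study enrollment, the investigators are to make additional follow-up C-SSRS observations".

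**The concern.** The protocol identifies a period of raised suicidality and then leaves its own suicidality instrument out of that period. By contrast, after each Experimental Session the form is given every other day for 14 days.

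What is at stake is timely recognition. Ideation that a participant does not volunteer, or that has not yet become serious, may meet no structured question until Visit 3. Participants withdrawn before Visit 3 may never meet one after taper starts. They include people who could not complete the taper, whom Table 9 says are withdrawn, and Protocol 4.4.3 schedules no further assessments for Pre-Treatment Early Terminations.

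**Working it through.** **1. Do other texts put a form in the gap?**

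- Table 9 says participants report suicidality through the C-SSRS in non-drug as well as MDMA sessions and on follow-up calls. Preparatory Sessions are non-drug sessions, so this contradicts footnote C. It names no visit.
- Table 5 ticks its Measures row at Visits 1 and 2 but refers to Table 6 for details, and Table 6 has none.
- Protocol 7.1.4 says items rated at IR Screening will be confirmed by clinical observation in the Preparatory Period and that the measures will not be repeated. Table 1 limits the no-repeat rule to the MINI.
- Protocol 6.3.1 says "Participants who are discontinuing medications to participate in the study will complete the C-SSRS before and after medication washout". IR Screening and Visit 3 can satisfy this with nothing between them.
- The Preparatory Session list in 7.2 mentions the form only at Visit 4, which is not a Preparatory Session.

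None of these schedules a form between IR Screening and Visit 3. The first two show that the documents disagree.

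**2. How long can the gap be?** Inputs:

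- IR Screening to Visit 0: 2 to 14 days (Table 1), or up to 30 (7.1.5)
- Visit 0 to Visit 1: 0 to 14 days (Table 1, 7.2.1)
- Visit 1 to Visit 2: 2 to 75 days (Table 1, 7.2.1)
- Between Preparatory Sessions: at least 48 hours (7.2)
- Visit 1 to Visit 3: 1 to 11 weeks (Table 1)
- End-of-taper call: up to 77 days after Visit 0 (Table 1)

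The plan's own figure first: 75 + 2 = 77 days = 11 weeks, which reproduces the Table 1 maximum for Visit 1 to Visit 3. Then:

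- Visit 0 to Visit 3: 14 + 77 = 91 days
- IR Screening to Visit 3: 14 + 91 = 105 days, or 30 + 91 = 121 with the 7.1.5 window
- Shortest, from IR Screening: 2 + 0 + 2 + 2 = 6 days from the visit spacings, or 2 + 0 + 7 = 9 with Table 1's one-week minimum

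Protocol 4.2 and 7.2 allow longer if the taper needs it, so 91 and 105 are sums of windows, not hard caps.

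**3. What does the stated average duration imply?** Protocol 4.2 expects the average participant to finish in 22 weeks: 22 × 7 = 154 days, taken here to run from consent. The minimum from consent to Visit 0 is 7 days. The minimum from Visit 3 to Visit 16 is 1 + 21 + 21 + 24 = 67 days.

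- Average Visit 0 to Visit 3: at most 154 − 7 − 67 = 80 days
- If sessions are 28 days apart and Visit 16 is 28 days after the third: at most 154 − 7 − (1 + 28 + 28 + 28) = 62 days

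These are upper bounds, because every other interval is set to its minimum or to monthly spacing. They are not estimates.

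**4. What would forms at Visits 1 and 2 leave?**

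- IR Screening to Visit 1: at most 14 + 14 = 28 days (30 + 14 = 44 with 7.1.5)
- Visit 1 to Visit 2: at most 75 days
- Visit 2 to Visit 3: at most 77 − 2 = 75 days

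Forms on taper calls shorten these to the interval between contacts.

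**The case against.** The strongest reply is that suicidality is watched throughout, by clinicians. The plan has these protections:

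- AEs and AESIs are collected from Visit 0.
- Eligibility is rechecked at Visits 1 and 2, and exclusion criterion 10 (Protocol 3.2) makes current serious suicide risk part of that recheck.
- Those visits are 90-minute sessions with a therapy pair, at least one of whom is licensed.
- Clinical observation is a stated substitute for repeating the measures (7.1.4).
- Tapers are closely monitored, and failed tapers are referred back to the prescriber for evaluation.
- Follow-up C-SSRS forms are given once serious ideation or behavior is known.
- The Visit 3 form looks back over the gap.

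All of this stands, and it rules out a reading that nobody monitors suicidality during taper or that failed tapers are abandoned. It does not supply a routine structured screen. AE information is elicited by open-ended questions (10.1). One AESI trigger is a C-SSRS ideation score of 4 or 5 (10.1.3), which needs the form. Exclusion criterion 10 relies partly on C-SSRS responses, yet no current form exists at Visits 1 and 2. Follow-up forms start only after recognition. The Visit 3 form comes late and reaches only those who get there. Protocol 10.1.7 asks for final-visit procedures after withdrawal where possible, but times them from the last dose, which these participants have not had.

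It is also fair that the maxima are extremes. Up to 14 of the 105 days precede Visit 0, when taper has not begun. Reaching 91 days needs Visit 1 at its latest and Visit 3 fourteen days after the latest end-of-taper call (77 + 14 = 91), although Visit 3 is due as soon as possible after taper. A reader might infer a three-month gap for most participants. The documents do not support that.

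Finally, forms at Visits 1 and 2 alone still leave up to 75 days. That is correct, and it is why the calls matter.

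**Conclusion.** The gap is real, and the sponsor should close it. The period that Table 9 flags for suicidality has no routine structured screen, and the schedule contradicts both Table 5 and Table 9's own account of C-SSRS use. Those withdrawn before Visit 3 have no planned form after taper starts.

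The size is up to 91 days from Visit 0 to Visit 3 at the Table 1 maxima, with an average of at most about 80 days if the 22-week figure is right and visit windows are kept. The documents do not say how many participants taper or for how long, so the typical gap cannot be stated.

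A reader might also infer that the planned C-SSRS tables are biased. The documents do not support this: never-dosed participants are outside the Safety set (SAP 8.1), and SAP 8.8.4 lists no preparatory time period. The point concerns safety monitoring. The wording of 6.3.1 and the Visit 4 reference in 7.2 are editorial matters only.

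**What to change.** - Tick the Since Last Visit C-SSRS at Visits 1 and 2 in Table 6 and in the SAP table, and delete footnote C in both. Table 5 and Table 9's statement then agree with the schedule.
- Amend 7.1.4 so that its rule against repeating measures does not cover the C-SSRS.
- Give the form on every taper or safety call that is made, including the end-of-taper call. Section 6.3.1 allows telephone administration.
- Offer it at the last contact of Pre-Treatment Early Terminations who agree, when the Exit Plan is given (7.4.2).
- Editorially, correct the Visit 4 reference in 7.2 and name the intended visits in 6.3.1.

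Cost: the form takes about 10 minutes. Visits 1 and 2 add 2 × 10 = 20 minutes per participant, or 100 × 20 = 2,000 minutes (about 33 hours) for 100 participants. Each call or exit contact adds 10 minutes. No new visit is needed. A protocol amendment with its reviews, an SAP table change and a data-capture update are. Because the taper calls are optional, a gap of up to 75 days can remain where none is made.
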